Relapsed/refractory pediatric solid and CNS tumors are a major cause of morbidity and mortality in pediatric oncology with few effective treatment options. Both preclinical and clinical studies involving pediatric solid and CNS tumors have shown an aberration of the mammalian target of rapamycin (mTOR) pathway. In addition, these studies have demonstrated that inhibition of the mTOR pathway has significant efficacy impeding growth of these tumors. ABI-009, also known as nab-Rapamycin, is a novel human albumin-bound preparation of rapamycin, a potent mTOR inhibitor. Albumin nanoparticle technology encapsulates lipophilic drugs into nanoparticles by combining drug and human serum albumin in a water-based solvent under high pressure. This technology enhances permeability and retention (EPR), allowing accumulation of macromolecules in solid tumors. In the adult phase 1 trial, ABI-009 was well tolerated with the most common toxicities including thrombocytopenia, mucositis, fatigue, rash, diarrhea, and hypertriglyceridemia. We will conduct a phase 1 trial of ABI-009 in combination with irinotecan and temozolomide in children with recurrent solid and CNS tumors using the Rolling Six design. The aims of the trial will be to establish the maximum tolerated pediatric dose of ABI-009, and to investigate the toxicities, pharmacokinetics, and pharmacodynamics of ABI-009 in children with these tumors.

EXPERIMENTAL DESIGN SCHEMA

Cycle 2+ Combination Therapy 21 Day Duration					
Day -2	Cefixime				PJP Prophylaxis
Day -1					
Day 1		TEMO	IRIN	ABI-009	
Day 2		TEMO	IRIN		
Day 3		TEMO	IRIN		
Day 4		TEMO	IRIN		
Day 5		TEMO	IRIN		
Day 6					
Day 7					
Day 8				ABI-009	
Day 9-19					
Day 20 ¹	Cefixime				
Day 21 ²		Evaluation			

TEMO: Temozolomide
 IRIN: Irinotecan
 PJP: Pneumocystis pneumonia

¹ Day 20 equals Day -2 of the following cycle.

² Day 21 equals Day -1 of the following cycle.

Treatment will be discontinued if there is evidence of progressive disease or drug-related dose-limiting toxicity that requires removal from therapy. Patients with stable disease or greater response may continue receiving protocol therapy provided that the patient meets the criteria for starting subsequent cycles ([Section 5.2](#)) and does not meet any of the criteria for removal from protocol therapy or off study criteria ([Section 10.0](#)).

1.0 GOALS AND OBJECTIVES (SCIENTIFIC AIMS)

1.1 Primary Aims

- 1.1.1 To estimate the maximum tolerated dose (MTD) and/or recommended Phase 2 dose (RP2D) of ABI-009 administered as an intravenous infusion over 30 minutes on Days 1 and 8 of a 21-day cycle, in combination with temozolomide and irinotecan (administered on Days 1-5) in pediatric patients with recurrent or refractory solid tumors, including CNS tumors.
- 1.1.2 To define and describe the toxicities of single-agent ABI-009 administered as an intravenous infusion over 30 minutes on Days 1 and 8 of a 21-day cycle in pediatric patients with recurrent or refractory solid tumors, including CNS tumors.
- 1.1.3 To define and describe the toxicities of ABI-009 administered as an intravenous infusion over 30 minutes on Days 1 and 8 of a 21-day cycle in combination with temozolomide and irinotecan (administered on Days 1-5) in pediatric patients with recurrent or refractory solid tumors, including CNS tumors.
- 1.1.4 To characterize the pharmacokinetics of ABI-009 in pediatric patients with recurrent or refractory solid tumors, including CNS tumors.

1.2 Secondary Aim

- 1.2.1 To preliminarily define the antitumor activity of ABI-009 in combination with temozolomide and irinotecan within the confines of a Phase 1 study.

1.3 Exploratory Aim

- 1.3.1 To assess the biologic activity of ABI-009 by examining SK61 and 4E-BP1 expression status in archival tumor tissue from solid tumor pediatric patients using immunohistochemistry.

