 - Autologous stem cell infusion including boost infusion: ≥ 42 days.
- h. Cellular Therapy: ≥ 42 days after the completion of any type of cellular therapy (e.g. modified T cells, NK cells, dendritic cells, etc.)
- i. XRT/External Beam Irradiation including Protons: ≥ 14 days after local XRT; ≥ 150 days after TBI, craniospinal XRT or if radiation to $\geq 50\%$ of the pelvis; ≥ 42 days if other substantial BM radiation.
- j. Radiopharmaceutical therapy (e.g., radiolabeled antibody, ^{131}I -MIBG): ≥ 42 days after systemically administered radiopharmaceutical therapy.
- k. Irinotecan, temozolomide and mTOR inhibitor exposure:
- i. Patients who have received prior single agent therapy with irinotecan, temozolomide, or an mTOR inhibitor, excluding ABI-009, are eligible.
 - ii. Patients who have received prior therapy with ABI-009 are not eligible.
 - iii. Patients who have previously received irinotecan and temozolomide in combination without progressive disease while on therapy are eligible.
 - iv. Patients who have previously received irinotecan and temozolomide in combination and had significant toxicity with these two drugs are not eligible.
 - v. Patients who have received prior therapy with all three agents in combination (i.e. irinotecan, temozolomide, and an mTOR inhibitor) are not eligible.

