4.1.9 Informed Consent: All patients and/or their parents or legally authorized representatives must sign a written informed consent. Assent, when appropriate, will be obtained according to institutional guidelines.

4.1.10 Tissue blocks or slides must be sent for all patients per [Section 8.4](#). If tissue blocks or slides are unavailable, the study chair must be notified prior to enrollment.

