Amylase, Lipase	X	Prior to Cycle 2	X
Pregnancy Test ²	X		
Tumor Disease Evaluation	X	End of Cycles 1 ¹² & 2	Every other cycle x 2 then q 3 cycles ⁵
Bone Marrow Evaluation ⁷	X		
Medication Diary ⁶		Cycle 2	X
Oxygen Saturation	X	Weekly	X ⁸
Tumor Tissue Studies ⁹	X		

[^] Studies may be obtained within 72 hours prior to the start of the subsequent cycle.

¹ See [Section 8.3](#) for timing of PK studies.

² Women of childbearing potential require a negative pregnancy test prior to starting treatment; sexually active patients must use an acceptable method of birth control. Abstinence is an acceptable method of birth control.

³ If patients have Grade 4 neutropenia then CBCs should be checked at least every 2-3 days until recovery to Grade 3 or until meeting the criteria for dose limiting toxicity.

⁴ If patients develop Grade 4 neutropenia or Grade 4 thrombocytopenia then CBCs should be checked every 3 to 4 days until recovery to Grade 3

⁵ Tumor Disease Evaluation should be obtained on the next consecutive cycle after initial documentation of either a PR or CR. Subsequent scans may restart 2 cycles after the confirmatory scan. Please note that for solid tumor patients, if the institutional investigator determines that the

- patient has progressed based on clinical or laboratory evidence, he/she may opt not to confirm this finding radiographically.
- ⁶ Medication diary (see [Appendix IX](#)) should be reviewed after completion of each treatment cycle and uploaded into RAVE.
- ⁷ As appropriate for disease, to confirm bone marrow involvement at enrollment, or as clinically indicated.
- ⁸ Required prior to each cycle; weekly for subsequent cycles only if clinically indicated.
- ⁹ See [Section 8.4](#) and [Appendix XII](#) for details of Tumor Tissue studies.
- ¹⁰ If Grade 3 or 4 hypercholesterolemia or Grade 3 or 4 hypertriglyceridemia is detected when routine (non-fasting) laboratory studies are performed, the tests should be repeated within 3 days in the fasting state to permit accurate grading.
- ¹¹ If the initial blood glucose is a random sample that is outside of the normal limits, then follow-up fasting blood glucose can be obtained and must be within the upper normal limits for age. If blood glucose is $\geq 250 - 500$ mg/dL or $> 13.9 - 27.8$ mmol/L when routine (non-fasting) laboratory studies are performed, the test should be repeated within 3 days in the fasting state to permit accurate grading.

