8.4 Tissue Studies (required)

The key objective of the tumor molecular profiling is to identify specific markers related to the mTOR pathway that may be predictive of response to ABI-009.

Archival tumor tissue (or unstained tissue slides) should be submitted for all patients. If a patient does not have tissue available, the study chair must be notified prior to enrollment.

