8.4.1 Description of Studies

8.4.1.1 Study of S6K1

Tumor tissue will be analyzed by immunohistochemistry. Antibody to be used for pS6(S235) is obtained from Cell Signaling, Catalog #2211S.

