APPENDIX XII: TISSUE STUDY FORM (REQUIRED TISSUE)

COG Pt ID # _____

Cycle 1, Day 1 Date: _____

Please do not write patient names on this form or on samples.

Body Surface Area: _____ m²

ABI-009 Dose Level: _____ mg/m²

ABI-009

Total Daily Dose: _____ mg

Tumor Sample Labeling:

Samples should be labeled with the following information:

Protocol number: ADV1514
Institution: _____
Patient ID #: _____
Accession #: _____
Sample Date: _____
Site of Acquired Tissue: _____
Tissue obtained at (check one option below):
 Diagnosis  Relapse

Shipment of Tumor Tissue:

Paraffin-embedded tumor specimens or tissue slides must be packaged appropriately and shipped at room temperature to the Specialized Histopathology Core at Brigham and Women's Hospital (at the address below). If a tumor block is not available, scrolls from the tumor block and/or 8-10 (minimum: 6) unstained slides may be shipped instead. Please indicate above the date of the sample, site of tissue acquisition and whether it was obtained at diagnosis or relapse. Shipments should be sent **Monday through Thursday only** for priority overnight delivery using the COG FedEx account (do not ship on Friday). One copy of this form should be uploaded into RAVE.

A second copy should be sent with the tissue sample to the lab address below.

Attn: Specialized Histopathology Core
Brigham and Women's Hospital
[name]
[name]
[name]
Attention: [name], Laboratory Manager

Notes: _____

If this form will be used as a source document, the site personnel who collected the samples must sign and date this form below:

Signature: _____
(site personnel responsible for samples)

Date: _____

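### Exploratory aim 1.3.1 claims to assess ABI-009's biologic activity from tissue that predates the drug; it should be reworded as a baseline-marker aim, in line with Section 8.4

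*Combined protocol and SAP*

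**What the plan says.** Section 1.3.1, the only exploratory aim, reads: "To assess the biologic activity of ABI-009 by examining SK61 and 4E-BP1 expression status in archival tumor tissue". It names immunohistochemistry as the method.

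Section 8.4 states the key objective of the same tissue work differently: "to identify specific markers related to the mTOR pathway that may be predictive of response to ABI-009". On collection it says: "Archival tumor tissue (or unstained tissue slides) should be submitted for all patients". Section 4.1.10 covers missing tissue: "If tissue blocks or slides are unavailable, the study chair must be notified prior to enrollment".

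For the assays, Section 8.4.1.1, headed as the study of S6K1, says: "Antibody to be used for pS6(S235) is obtained from Cell Signaling". Section 8.4.1.2, headed as the study of 4E-BP1, lists an antibody to p4EBP1.

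Section 11.5 limits the correlative biology analyses to exploratory description that may raise hypotheses. It names no summary of staining against response. The abstract, before the design schema, includes pharmacodynamics among the things the trial will investigate.

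**The concern.** Assessing a drug's biologic activity means seeing what changed after the drug was given. Tissue taken before the first dose describes the tumor's mTOR-pathway status at that time and holds no information on what ABI-009 later did to it. If the aim were followed literally, a staining result from archival tissue would be reported as evidence of ABI-009 activity, and that conclusion would be unsupported. The formal aim also disagrees with Section 8.4, so a reader cannot tell which question the tissue is meant to answer.

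**Working it through.** No power, alpha or sample-size figure is attached to this aim, so there is no plan figure to reproduce. The check compares the aim with specimen timing, then counts samples.

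**1. Can any tissue be post-exposure?**

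- Section 4.1.7.1.k: "Patients who have received prior therapy with ABI-009 are not eligible". Tissue archived before enrollment therefore cannot have been exposed to ABI-009.
- Section 8.1 schedule: the row "Tumor Tissue Studies" has one mark, in the pre-study column, and none in Cycles 1 and 2 or later.
- Sections 4.1.10 and 8.4: whether tissue exists is settled before enrollment.
- Appendix XII: the form asks "whether it was obtained at diagnosis or relapse" and offers no on-treatment option.

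Planned post-exposure tumor samples: 0.

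**2. Could blood serve instead?** Section 2.3.3 reports that the adult study showed drug effect through circulating S6K1 and 4EBP1 followed after dosing. To see whether this trial has an equivalent:

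- ABI-009 pharmacokinetics (Section 8.3.2.1, Appendix XI-A): 9 samples × 2 cycles = 18.
- Irinotecan pharmacokinetics (Section 8.3.2.2, Appendix XI-B): 6 samples.
- Volume: (18 + 6) × 2 ml = 24 × 2 ml = 48 ml.
- Appendix II total for Cycles 1 and 2: 48 ml.

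The two totals agree, so all scheduled correlative blood is pharmacokinetic. Pharmacodynamic blood samples: 0.

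**3. Do the two stated purposes agree?** Section 1.3.1 asks what ABI-009 does. Section 8.4 asks which baseline markers go with response. Only the second can be addressed with pre-study tissue.

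**4. How far can the Section 8.4 purpose go?** Section 5.3.1 adds irinotecan and temozolomide from Cycle 2, and there is no control arm. The end-of-Cycle-1 evaluation follows ABI-009 alone. Under Section 12.7.1, however, any best response other than progression at the first assessment needs a second assessment, which falls after the combination has started. An association between staining and best response therefore cannot be credited to ABI-009 or separated from prognosis.

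**5. How many responders?** Section 2.1.4 gives two rates for related regimens. Both are borrowed from other studies and serve as illustrations only. Enrollment is from Section 11.1.1: expected maximum 36, absolute maximum 44.

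| Source of rate | Rate | × 36 | × 44 |
|---|---|---|---|
| Temsirolimus with irinotecan and temozolomide, mixed solid tumors | 6/71 = 8.5% | 3.0 | 3.7 |
| Irinotecan and temozolomide alone, neuroblastoma | 8/50 = 16% | 5.8 | 7.0 |

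The first row is the closer match in regimen and population. On either rate, a marker-by-response listing would hold only a handful of responders, and fewer if tissue is missing.

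**The case against.** The timing point has no rebuttal in the documents. The objections concern how much rests on it, and several stand.

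- **Wrong protein.** A reader might infer that the assay measures the wrong protein, which would be a second reason the aim fails. The documents do not support that. SK61 in Section 1.3.1 is evidently a transposition, since Section 2.1.1 and Section 8.4.1.1 use S6K1. The pS6(S235) antibody is listed under the S6K1 heading, and Section 2.1.1 describes S6K1 as the S6 kinase, so phospho-S6 appears to be meant as its readout, although the protocol does not say so. 4E-BP1 is measured in phosphorylated form, and Section 2.1.1 itself says phosphorylation status is used to assess mTORC1 activity. The assays suit the pathway; the loose word is expression.
- **Tissue collected for nothing.** A reader might also infer this. It does not follow: Section 8.4 gives the tissue a use it can serve, submission is excused when none is available, and no biopsy is added for the study.
- **No analysis specified.** A descriptive exploratory aim in a phase 1 trial needs no formal test, so the silence of Section 11.5 is not an error in itself. A listing is still worth adding, because without it the purpose in Section 8.4 has no stated output.
- **Low consequence.** This is right. Section 11.5 already restricts the correlative work to description, and no dose-limiting toxicity rule or dose decision uses the staining.

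**Conclusion.** The aim cannot be answered as written. It states a drug-effect objective, and the number of planned specimens able to show such an effect is zero, so no sample size would help. It also conflicts with Section 8.4, and the abstract's mention of pharmacodynamics has the same lack of support.

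The defect is one of wording and alignment, and its severity is low. The dose-finding, toxicity, pharmacokinetic and antitumor-activity aims are untouched. The conclusion rests on the specimen schedule in Sections 8.1, 8.3 and 8.4 and in Appendices II, XI-A, XI-B and XII being complete. The responder counts assume that response rates from related regimens carry over; they show the likely scale and are not forecasts.

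**What to change.** 1. **Section 1.3.1:** describe baseline pS6(S235) staining, stated to be the readout of S6K1 activity if the sponsor confirms that intent, and baseline p4E-BP1 staining in archival tissue. Explore descriptively the association with best response to the regimen. Drop the biologic-activity claim. As a minor correction, change SK61 to S6K1 and expression to phosphorylation status.
2. **Section 8.4:** make the response of interest that to the regimen, and say that an association cannot be attributed to ABI-009 or separated from prognosis.
3. **Abstract:** remove or qualify pharmacodynamics.
4. **Section 11.5:** add a listing of staining by best response that notes tissue source and prior mTOR-inhibitor exposure. Section 4.1.7.1.k allows earlier single-agent treatment with other mTOR inhibitors, so relapse tissue may reflect those drugs. State that few responders are expected and that the result is descriptive only.

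The cost is edited wording and one listing, with no new samples or assays. Appendix XII already records tissue source, and prior mTOR-inhibitor therapy has to be reviewed for eligibility. Keeping a true biologic-activity aim would instead need paired specimens from before and after dosing, which the trial does not collect.

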2.0 BACKGROUND

2.1 Introduction/Rationale for Development

2.1.1 ABI-009 and the mTOR Pathway

ABI-009, also known as *nab*-Rapamycin, is a novel human albumin-bound preparation of rapamycin, a potent mammalian target of rapamycin (mTOR) inhibitor. Rapamycin interacts with the 12 kDa FK506-binding protein (FKBP12) and forms a gain-of-function complex, resulting in inhibition of mTOR function.¹ Aberration of the mTOR pathway occurs in numerous adult and pediatric cancers as a result of gain-of-function mutations in oncogenes and/or loss-of-function mutations in tumor suppressors.¹ The deregulation of the mTOR pathway is not only confined to cancer, but also observed in obesity, type 2 diabetes, and neurodegeneration.²

mTOR, a serine/threonine protein kinase, belongs to the phosphoinositide 3-kinase (PI3K)-related protein kinase family because of the homology its C-terminus shares with the catalytic domain of PI3K.² It is composed of two functionally separate protein complexes, mTOR complex 1 (mTORC1) and 2 (mTORC2), that have varying upstream inputs and downstream outputs as well as sensitivity to rapamycin, with mTORC1 being the more sensitive complex.³ Once activated, mTORC1 directly phosphorylates the translation regulators p70 ribosomal S6 kinase 1 (S6K1) and eukaryotic inhibition factor eIF4E binding protein 1 (4E-BP1) resulting in nucleotide and protein synthesis.⁴ Additionally, phosphorylation status of S6K and 4E-BP1 are frequently used to assess mTORC1 activity *in vivo*.³ Conversely, the underpinnings of mTORC2 role and function are yet to be fully understood. mTORC2 is thought to be rapamycin insensitive; however, long-term exposure in certain cell types reduces mTORC2 signaling.⁵

2.1.2 mTOR Signaling in Cancer

The mTOR pathway has numerous roles in cancer pathogenesis. Aberrant activation of this pathway, either by gain-of-function mutations in oncogenes and/or loss-of-function mutations in tumor suppressors, results in tumor growth, angiogenesis, resisting cell death, and metastasis.⁶ One signaling pathway altered in multiple cancer types is the PI3K/AKT kinase cascade, which is the key kinase acting upstream of both mTORC1 and mTORC2. The PI3K/AKT signaling cascade is deregulated by multiple mechanisms some which include mutations in PI3K, mutations or amplifications of AKT, overexpression of growth factor receptors human epidermal growth factor receptor 2 (HER-2), insulin-like growth factor receptor (IGFR), and platelet-derived growth factor receptor (PDGFR), or loss of phosphatase and tensin homolog (PTEN) function.^{3,6} mTOR downstream effectors S6K1, 4EBP1, and eIF4E are also implicated in tumorigenesis; however, their exact mechanisms of tumorigenesis are yet to be elucidated. Tumor formation is not only a consequence of aberrant activation of the mTOR pathway, but is also a result of familial cancer syndromes that interact upstream from this pathway; specifically, Peutz-Jeghers syndrome (mutation of the serine threonine kinase 11 (Lkb1)), Tuberous Sclerosis (mutations in the TSC1 or TSC2), and Cowden disease (loss of PTEN function).³

The overall survival for advanced stage or refractory pediatric intracranial and extracranial solid tumor malignancies remains dismal.⁷ The PI3K/AKT/mTOR pathway has been implicated in several pediatric solid tumor malignancies. These findings are outlined below:

- **Neuroblastoma (NB):** Overexpression of PI3K p85, PI3K p110, p-Akt, and p-mTOR, and decreased PTEN expression, as well as, Akt activation have been identified as poor prognostic indicators.^{8,9}
- **Osteosarcoma (OS):** The PI3K/AKT pathway has been shown to be deregulated in a majority of localized OS and in 100% of advanced-stage disease.¹⁰ In addition amplification of the oncogene c-Myc is seen in approximately 10% of OS and upregulated by Akt phosphorylation, while cyclin D1 is overexpressed in 20% of OS and is a downstream target of mTORC1.¹¹ Investigators have also shown that *in vitro* mTOR inhibition decreases proliferation, while *in vivo* delays tumor progression and pulmonary metastasis.¹²

- **Ewing Sarcoma (EWS):** EWS has a distinctive karyotypic abnormality involving the EWSR1 locus forming a fusion product with Fli-1, ERG, ETV1, or E1AF. These fusion proteins act as aberrant transcription factors and in *in vitro* studies have been shown to interact with insulin like growth factor 1 (IGF-1). IGF-1 indirectly activates PI3K through Ras signaling and via insulin receptor substrate 1 (IRS-1) leading to downstream activation of mTOR signaling.¹³ All EWS family of tumors express the IGF-1 receptor and this suggests a potential role for IGF-1 in tumorigenesis.¹³
- **Rhabdomyosarcoma (RMS):** The chromosomal translocation involving the FOXO1 gene and the PAX3 or PAX7 gene occur in approximately 80% of alveolar RMS (ARMS), and are known to play a vital role in cell cycle dysregulation and tumorigenesis.¹⁴ The PAX3-FOXO1 translocation decreases PTEN expression resulting in PI3K/Akt activation.¹³ The Children's Oncology Group analyzed 64 primary RMS tumors via microarray and noted phosphorylated mTOR levels were increased in 60% of ARMS and 68% of embryonal RMS (ERMS) cases.¹³
- **Medulloblastoma (MB):** Recent studies have linked the sonic hedgehog (SHH) signaling pathway as an important mediator in the activation of the mTOR pathway and its downstream effectors S6K and eIF4E.¹⁵
- **Gliomas:** The signaling pathways that trigger the pathogenesis of pediatric gliomas have yet to be understood. Mueller et al. investigated the PI3K/Akt/mTOR pathway in low- and high-grade pediatric gliomas. Their study revealed that 80% of high-grade pediatric gliomas and 40% of low-grade gliomas showed activation of the PI3K/Akt/mTOR pathway and also suggested the tumor grade correlated negatively with PTEN expression.¹⁶
- **Renal Tumors:** Currently, initial treatment for metastatic renal cell carcinoma involves mTOR inhibition.¹⁷ mTOR's role in Wilms' tumor is less defined; however, one study did reveal activation of the mTOR-signaling pathway in a metastatic lung lesion in a patient with Wilms' tumor.¹⁸
- **Hepatic Tumors:** Both hepatoblastoma and hepatocellular have deregulation of PI3K/Akt/mTOR signaling pathways resulting in tumorigenesis.^{19,20}

